7.8.2. Exploratory Biomarkers of Asthma

Serum samples will be collected during this study and may be used for the purposes of measuring biomarkers to identify factors that may influence the development of asthma and/or medically related conditions or the development of asthma treatments, as well as the biological and clinical responses to GSK3511294. Samples will be collected at the time points indicated in Section 7.1, Time and Events Table.

All exploratory biomarker samples will be retained for a maximum of 15 years after the last participant completes the trial.

7.9. Genetics

Information regarding genetic research is included in [Appendix 4](#). Participant participation is optional. Participants who do not wish to participate in the genetic research may still participate in the study.

8. DATA MANAGEMENT

- For this study participant data will be entered into GSK defined CRFs, transmitted electronically to GSK or designee and combined with data provided from other sources in a validated data system.
- Management of clinical data will be performed in accordance with applicable GSK standards and data cleaning procedures to ensure the integrity of the data, e.g., removing errors and inconsistencies in the data.
- AEs and concomitant medications terms will be coded using MedDRA and an internal validated medication dictionary, GSK Drug.
- CRFs (including queries and audit trails) will be retained by GSK, and copies will be sent to the investigator to maintain as the investigator copy. Participant initials will not be collected or transmitted to GSK according to GSK policy.
- Participant initials and full date of birth will not be collected in the CRF or transmitted to GSK, according to GSK policy.

9. STATISTICAL CONSIDERATIONS AND DATA ANALYSES

9.1. Hypotheses

Given this study is the FTIH for GSK3511294, there are no formal statistical hypotheses to be tested. The assessment of safety and tolerability of single SC doses of GSK3511294 in this study will not include any formal comparisons. For the pharmacokinetic and pharmacodynamic data, where appropriate, an estimation approach will be adopted and point estimates with corresponding confidence intervals will be provided. In addition, for the analysis of blood eosinophils, posterior means and corresponding 95% credible intervals will be constructed for each dose and time point. Furthermore, posterior probabilities that the placebo adjusted ratio is less than various thresholds of interest will be constructed.

9.2. Sample Size Considerations

No formal statistical techniques were used to calculate the sample size for this study. The number of participants included is primarily determined by feasibility and is deemed an adequate number to provide an assessment of safety and tolerability, pharmacokinetics and pharmacodynamic measurements, and thereby to allow progression to larger clinical studies. More participants are planned in cohorts to be given doses in the expected therapeutic range to gain more information on those dose levels.

9.2.1. Sample Size Assumptions

Although the sample size is not based on statistical criteria, general probabilities can be determined on the likelihood of seeing adverse events. For example, with 6 participants receiving each dose of active drug, if the true adverse outcome rate is 5%, the chance of seeing at least one adverse outcome at a given dose is 26%. Similarly, if the true adverse

outcome rate is 20%, the chance of seeing at least one adverse outcome at a given dose is 74%. The corresponding figures for 9 participants with true event rates of 5% and 20% are 37% and 87%, respectively. This level of predictivity is deemed adequate within this FTIH setting, prior to progression to larger studies.

9.2.2. Sample Size Re-estimation or Adjustment

No formal sample size re-estimation will be performed. However, upon ongoing review of data, it is possible that the size of a cohort may be increased.

9.3. Data Analysis Considerations

Statistical analysis will be performed by, or under the direct auspices of Clinical Statistics, GlaxoSmithKline.

Complete details of the planned statistical analyses will be provided in the RAP.

9.3.1. Analysis Populations

For purposes of analysis, the following populations are defined:

- Screened: All participants who were screened.
- Safety: All randomised participants who take at least 1 dose of study treatment. Participants will be analysed according to the treatment they actually received.
- Pharmacokinetic: Participants in the ‘Safety’ population for whom a pharmacokinetic sample was obtained and analysed.
- Pharmacodynamic: Participants in the ‘Safety’ population for whom a post-dose pharmacodynamic (i.e. blood eosinophil) sample was obtained and analysed.

9.3.2. Interim Analyses

In stream data review will occur during the study to support dose escalation decisions, and formal interim analyses are planned to ensure accumulated safety, PK and PD data are deemed sufficient to determine the doses and dosing interval to move forward into the next phase of development but is not expected to affect the progression of this FTIH study.

Currently, the first interim analysis is projected to occur once data is available at the 12-week time point after dosing in Cohort 4 (planned 100 mg dose). The primary focus of this interim analysis will be reduction in blood eosinophil counts. The ratio to baseline will be derived for each dose and time point and will be compared to corresponding data from the placebo arm. Posterior means and corresponding 95% credible intervals will be constructed for each of the available doses and time points. Furthermore, posterior probabilities that the placebo adjusted ratio is less than various thresholds of interest will be constructed.

The earliest next interim analysis is planned no earlier than once data is available at the 26-week time point after dosing Cohort 4 (planned 100 mg dose). The primary focus of

this and potential subsequent interim analyses will be the same as the first interim analysis (described above).

The interim analyses will be performed by GSK Clinical Statistics and only the responsible statistician (and Quality control [QC] statistician) and the CPMS representative will have access to individual participant data. However, the findings of the interim analyses will be shared with the entire GSK study team.

9.4. Key Elements of Analysis Plan

On-going PK analyses will be performed on plasma concentration-time data available prior to dose escalation decisions in subsequent cohorts.

For these on-going analyses, plasma concentration-time data will be analysed by non-compartmental methods using nominal times. The decision to proceed to higher doses will be made by the Dose Escalation Committee based on assessment of safety/tolerability and PK data at lower dose levels, together with any available PD data if deemed appropriate.

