4.3. Dose Escalation

- The Dose Escalation Committee (DEC) will consist of the Principal Investigator(s) (or appropriate designee), GSK Medical Monitors, GSK Study Team Leader, GSK Clinical Pharmacology Modelling and Simulation (CPMS) representative, a GSK Global Clinical Safety and Pharmacovigilance (GCSP) representative and GSK Statistician representative. The GSK CPMS and statistician representatives will remain unblinded throughout the course of the study.
- The DEC will select and approve doses throughout the study, and will review available data from all participants in each cohort before initiating each new dose level. Dose escalation may occur only after review of the following data at the highest dose level tested to date: at least 4 weeks' post-dose safety data and at least 2 weeks' post-dose PK data from at least 4 participants on active treatment; and at least 72 hours' post-dose safety data from the remaining participants in the cohort. In the unlikely event that one or more of the remaining participants discontinued the study within 72 hours after dosing, all available safety data from that/those participants will be reviewed.
- Owing to the mechanism of action of GSK3511294, blood eosinophil results have the potential to unblind. Therefore, study personnel will be blinded to post-dose blood eosinophil results for individual participants. The sponsor CPMS and statistician representatives will review individual data, but summary statistics for the active group only will be provided to the remaining members of the DEC for the purposes of dose selection. Similarly, to minimise the risk of unblinding during DEC meetings, no individual PK data will be discussed; summary statistics only will be provided to blinded members of the DEC. If ongoing analyses are based on an incomplete cohort, to avoid unblinding, the DEC (except the GSK CPMS and statistician representatives) will be blinded to the number of participants included in the summaries of PK and blood eosinophils for that cohort.
- This protocol allows some alteration from the currently outlined dosing schedule, but the maximum single dose will not exceed 300 mg.
- The dose will be increased only if safety and tolerability at previous dose levels are acceptable, and also if the predicted exposure (upper 95% prediction interval for C_{max} and AUC) at the next dose level does not exceed the mean exposure observed at the NOAEL in monkey in the 26 week toxicity study (100 mg/kg).

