mean C_{max} : 1390 $\mu\text{g}/\text{mL}$	mean AUC_{0-2016} 1120000 $\mu\text{g} \cdot \text{h}/\text{mL}$
---	--

- one or more of the study halting criteria are met (see Section 5.5)
- one or more participants has experienced at least one of the criteria for potential type III hypersensitivity/immune complex disease, and there is ongoing clinical concern about the participant's condition (see Section 5.4.2)
- one or more participants has a QTcF > 500 msec or uncorrected QT > 600 msec, or an increase in QTcF > 60 msec, in the absence of any other identifiable reason (e.g. concomitant medication). In such a scenario, if after review of all clinical safety data for the participant(s), the increased QT is considered to be isolated and not clinically significant in the opinion of the medical monitor and investigators, dose escalation and/or dosing of further patients at the dose level at which the event was observed can occur only after ethics and regulatory approval of a substantial amendment.

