4.6. Dose Justification

Pharmacokinetics: Mepolizumab and GSK3511294 plasma concentration data, generated from a single dose cynomolgus monkey PK/PD study, were modelled simultaneously along with the toxicokinetics (TK) data from the one month toxicity study, and showed that only systemic clearance differed between the two molecules. The volume of distribution of the central and peripheral compartment, as well as the inter-compartmental clearance, were similar. Clearance decreased by an estimated 1.9-fold with GSK3511294 compared to mepolizumab, and this fold reduction is expected to be preserved between monkey and human. Predicted human exposure following single GSK3511294 SC administration at the proposed doses in the study were estimated using the known mepolizumab PK in human adjusted by the predicted fold difference in clearance determined from the pre-clinical studies (Table 1 and Figure 3). Absolute bioavailability was assumed to be 75%, similar to mepolizumab. The predicted human systemic clearance (CL) is 0.00465 L/h or 0.112 L/day and the plasma elimination half-life is approximately 37 days.

IL-5 binding affinity: Due to the limitation of various *in vitro* assays, GSK3511294 binding affinity is difficult to measure, but is anticipated to be 20-30 fold more potent than mepolizumab. Simulations to reproduce the total IL-5 and blood eosinophil profiles observed in the cynomolgus monkey PK/PD study were generated using a PK/PD model developed previously based on mepolizumab pharmacology data. Whilst acknowledging the uncertainty due to the small sample size in the cynomolgus monkey study, simulations seem to support a minimum of a 30-fold higher binding affinity of GSK3511294 compared with mepolizumab.

Estimation of GSK3511294 therapeutic dose and frequency of administration: The approved mepolizumab therapeutic dose in severe eosinophilic asthma is 100 mg SC administered every 4 weeks. It is hypothesised that if the blood eosinophil reduction observed at GSK3511294 trough concentrations in steady-state conditions is similar to that observed at mepolizumab 100 mg SC trough concentrations, it is likely that similar ‘clinical efficacy’ (reduction in asthma exacerbations) to mepolizumab will also be

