Maximum GSK3511294 dose: In this single ascending dose FTIH study, the maximum proposed GSK3511294 SC dose is 300 mg which is 23-fold lower than the NOAEL dose established in the 26-week toxicity monkey study (dose expressed in mg/kg and assuming a 70 kg participant). This dose will provide safety data at a dose 3-fold above the upper limit of the predicted therapeutic GSK3511294 SC dose range of 30–100 mg for severe asthma (predicted based on the GSK3511294 monkey PK/PD data). A dose of 300 mg remains operationally feasible and is expected to be tolerated by participants with regard to number of injections (3x100 mg SC injections). Furthermore, the proposed 300 mg maximum GSK3511294 SC dose, with an estimated average maximum reduction in blood eosinophils of approximately 93% (Figure 4), is anticipated to be tolerable given that 750 mg Intravenous (IV) mepolizumab administered every 4 weeks for at least 12 months (average 88% blood eosinophil reduction at lowest concentration of a drug just before the next dose [Ctrough]) was found to be well tolerated. Redundancy mechanisms exist to promote eosinophil production and therefore a complete (100%) suppression of blood eosinophils is not expected even at the maximum proposed 300 mg SC dose of GSK3511294. The predicted AUC at this dose is 23-fold lower than the exposure observed at the NOAEL dose of 100 mg /kg in the 26 week toxicity monkey study (Table 1).

Figure 3 Predicted mean with 95% CI GSK3511294 plasma concentration-time profiles at the planned single SC doses of 2, 10, 30, 100 and 300 mg (with mepolizumab as a reference)

[figure not shown]

Figure 4 Predicted mean with 95% CI GSK3511294 blood eosinophil ratio-time profiles at the planned single SC doses of 2, 10, 30, 100 and 300 mg (with mepolizumab as a reference)

[figure not shown]

Table 1 Safety margins when comparing monkey NOAEL data (cross-reactive species) with predicted human data at the proposed doses of GSK3511294 administered SC ('safety cover')

Predicted Human Cmax and AUC				Safety cover (vs. Monkey NOAEL)		
Dose (mg)	Dose (mg/kg) ¹	Cmax (µg/mL)	AUC (µg*h/mL)	Dose cover ²	Cmax Cover	Cover AUC
2	0.03	0.226	323	3500x	6156x	3471x
10	0.14	1.13	1613	700x	1231x	694x
30	0.43	3.39	4840	233x	410x	231x
100	1.43	11.3	16132	70x	123x	69x
300	4.29	33.9	48396	23x	41x	23x

1. assuming a 70 kg participant

2. dose (expressed in mg/kg) cover

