	
spermatogenic cycle and the integrity of the various cell types present within the different stages in sexually mature males. No cell or stage specific abnormalities were noted. In addition, there is a low reproductive risk associated with the IL-5 target mechanism (as shown in pre-clinical reproductive toxicology studies of mepolizumab and reslizumab), a low genotoxic concern for mAbs in general, and a low transfer of monoclonal antibody (mAbs) into semen due to the inability of large molecular weight proteins such as GSK3511294 to access pivotal cells in the testes [Setchell, 1975; Pollanen, 1995; Pollanen, 1989; Setchell, 2001; Sohn, 2015], the risk of adverse effects on spermatogenesis is considered minimal.
	
 It is expected that spermatogenesis will not be affected by GSK3511294, so males will not be required to use contraception during the study.
Study Design		

 Duration of in-patient stay after dosing 	
 Tmax of GSK3511294 is expected at 7–10 days after dosing. However, any significant side effect of GSK3511294 in the time to Tmax is most likely to be an anaphylactic reaction, which would occur in the first 72 hours after dosing. The predicted PK profile indicates approximately 80% of Cmax at 72 hours after dosing. Participants will have a minimum 72 hour in patient monitoring period at experienced phase 1 study. 	
 In the UK, Investigators will review available safety data up to 72 hours to confirm participants are well enough to leave the clinical unit. In Germany, in response to regulatory comments, participants will be in-patient until at least 8 days after dosing. Participants will receive a medical alert card, with details of the study, clinical site and Investigator, when they are discharged from the unit. They will be instructed to

Potential Risk of Clinical Significance	Summary of Data/Rationale for Risk	Mitigation Strategy
	
Therefore, to minimise the inconvenience to participants, they may be discharged from the clinical unit 72 hours (or longer) after dosing, provided that the Investigator considers them well enough to leave.
	
contact the unit with any safety concerns they might have, and to show the medical alert card to any other medical professional they might consult.

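### Can non-compartmental analysis of as little as two weeks of PK data serve the AUC half of the dose-escalation cap?

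*Protocol*

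**What the plan says.** Protocol 4.3 (Dose Escalation) permits a higher dose only when the upper 95% prediction limit for Cmax and AUC "at the next dose level does not exceed the mean exposure observed at the NOAEL in monkey". The AUC limit is given as "mean AUC_{0-2016} 1120000" µg.h/mL. No interval is attached to the human AUC. The minimum PK evidence is two weeks of "post-dose PK data from at least 4 participants on active treatment". The same sentence requires at least four weeks of safety data.

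Protocol 9.4 (Key Elements of Analysis Plan) says of the analyses run before escalation decisions that "plasma concentration-time data will be analysed by non-compartmental methods using nominal times". It does not describe how a next-dose prediction, or its 95% limit, is formed.

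Protocol 4.6 (Dose Justification) does describe a prediction. Human exposure was taken from known mepolizumab PK, "adjusted by the predicted fold difference in clearance determined from the pre-clinical studies", with bioavailability 75%, clearance 0.00465 L/h, and "the plasma elimination half-life is approximately 37 days". Table 1 sets the resulting AUC at each dose against the monkey value. For 300 mg, "The predicted AUC at this dose is 23-fold lower than the exposure observed at the NOAEL dose".

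**The concern.** Read side by side, the two sections do not seem to meet. The limit is an 84-day AUC, the data may stop at Day 15, and the one method named for those data needs a terminal slope to go beyond the last sample. With tmax expected at 7-10 days, only the Day 15 sample clearly lies after the peak.

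Two things could go wrong. An AUC over two weeks might be set against a limit over twelve, which flatters the drug. Or a slope from Day 8 to Day 15 might be extrapolated, giving a number with little information in it. Either would weaken a safety rule in a first-in-human study of an antibody designed to clear slowly, with the size of that slowing carried over from monkey.

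**Working it through.** **1. The protocol's own figure.** Inputs from 4.6: F = 0.75, CL = 0.00465 L/h. F x dose / CL gives 0.75 x 300 / 0.00465 = 48,387 µg.h/mL against 48,396 in Table 1, and 322.6 against 323 at 2 mg. Table 1's unlabelled AUC is therefore AUC(0-infinity). Cover at 300 mg is 1,120,000 / 48,396 = 23.1, as stated. The limit's window is 2016 / 24 = 84 days.

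**2. What two weeks show.** Assumed model: one compartment, first-order absorption, ke = ln 2 / 37 per day, ka solved from tmax = ln(ka/ke)/(ka - ke). The share of AUC(0-infinity) reached by T is 1 - [ka exp(-ke T) - ke exp(-ka T)]/(ka - ke). Day 15 is T = 14 and Day 29 is T = 28.

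| tmax | 7 d | 8 d | 10 d |
|---|---|---|---|
| ka per day | 0.483 | 0.402 | 0.294 |
| C(72 h)/Cmax | 84% | 79% | 68% |
| AUC to Day 15 / AUC(0-infinity) | 20.0% | 19.3% | 17.9% |
| AUC(0-84 d) / AUC(0-infinity) | 78.4% | 78.3% | 77.9% |
| AUC(0-84 d) / AUC to Day 15 | 3.9 | 4.1 | 4.3 |
| Half-life from Day 8-15 | 52 d | 75 d | none (still rising) |
| Extrapolated / true AUC(0-infinity), Day 15 | 1.3 | 1.8 | not estimable |
| Same, using Day 29 | 1.004 | 1.011 | 1.055 |

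Section 4.7.1 states that "The predicted PK profile indicates approximately 80% of Cmax at 72 hours after dosing", which favours the first two columns.

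**3. Clearance at half the prediction (V and ka unchanged, tmax 7-8 d).** AUC to Day 15 rises 6% and Cmax 5-6%, while AUC(0-84 d) rises 36-37% and AUC(0-infinity) doubles. Cover at 300 mg falls to 1,120,000 / 96,774 = 11.6 on the infinite basis. Extrapolating from Day 8-15 gives 2.1 to 17 times the true AUC(0-infinity).

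**4. A bound that needs no model.** AUC(0-2016 h) cannot exceed Cmax x 2016 h. To reach the limit, Cmax would have to exceed 1,120,000 / 2016 = 556 µg/mL. Table 1 predicts 33.9 µg/mL at 300 mg, and 556 / 33.9 = 16.4. Cmax is due at 7-10 days, so two weeks of observed data already constrain the matched 84-day AUC.

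**5. The cap is on an upper limit, not a mean.** The protocol gives no between-participant variability, so a range is assumed. With log-normal AUC and only four participants, the upper limit is the geometric mean times exp(3.182 x s x sqrt(1 + 1/4)) = exp(3.558 s), where s = sqrt(ln(1 + CV²)) and 3.182 is the t quantile on 3 degrees of freedom.

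| CV | Factor | Cover left from 23.1 | From 11.6 |
|---|---|---|---|
| 30% | 2.8 | 8.1 | 4.1 |
| 50% | 5.4 | 4.3 | 2.2 |
| 70% | 9.5 | 2.4 | 1.2 |

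**6. Data in hand where the margin is smallest.** AUC cover is 694x, 231x, 69x and 23x for the steps to 10, 30, 100 and 300 mg. Each step requires four weeks of safety follow-up. Under the planned order, when 300 mg is considered the first four active participants at 10 mg are at least 3 x 4 = 12 weeks past dosing, and those at 2 mg at least 16 weeks. Table 4 samples both groups to Day 183. Once those samples are assayed, AUC to Week 12 can be observed directly at two doses. A Day 29 sample is also scheduled at every dose level.

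**The case for a change.** The strongest case for a change is that the cap is a protocol rule governing who is dosed, so its inputs belong in the protocol. Section 9.4 itself fixes a method for the on-going analyses, so pointing to the reporting and analysis plan is not a full answer. The amendment history records that the prediction limit was adopted after a regulator objected to mean PK data, yet no step producing that limit is described. And step 3 shows that two-week partial AUC and Cmax hardly move when clearance is halved, which is the departure an AUC rule should detect.

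Part of this stands. The human AUC interval has to be inferred from Table 1, and the prediction step is not written down.

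The rest does not carry. Section 4.3 asks for a predicted exposure at a dose not yet given, and section 9.4 describes the handling of concentrations already measured. These are different tasks, and neither section makes non-compartmental output the sole input to the cap. An unblinded modelling and simulation representative sits on the committee and reviews individual data, and section 4.6 already contains a prediction route.

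Setting a two-week AUC against the twelve-week limit would understate exposure about 4-fold on matched windows and 5-fold or slightly more against AUC(0-infinity). It could pass a breach only if true AUC(0-infinity) were 23 times the prediction. Extrapolation from Day 8-15 errs upwards, towards not escalating. Its extreme case (halved clearance, tmax 8 d) would read about 17 x 96,774 = 1.6 million µg.h/mL at 300 mg and could wrongly hold the dose. That figure would be about 99% extrapolated, a percentage the protocol lists among its PK parameters, and using it would mean ignoring Day 29 and all earlier cohorts.

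**Conclusion.** No change is needed. This is a gap that analysts fill sensibly, not a contradiction. On the protocol's predictions the mean AUC at the top dose is 23-fold below the limit on the stricter AUC(0-infinity) basis, and about 29.5-fold below it on matched 84-day windows. It stays about 11.6-fold below with clearance halved. None of the cases worked through lets an exposure above the limit pass. Writing down the interval and the prediction step would record what the committee's modelling representative would do anyway.

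The conclusion assumes a one-compartment profile, although section 4.6 describes a two-compartment one; the Cmax bound in step 4 does not depend on this. It also assumes roughly dose-proportional PK, a between-participant CV no higher than about 70% at the four-participant minimum, and that PK results already in hand from earlier cohorts are used. It takes no position on the cap, the doses or the minimum follow-up.
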